## ADAPT-AST Protocol

[figure not shown]

Figure 5: Algorithmic schema for categorisation of antimicrobial results according to whether the clinician 'should', 'could', or cannot action them. In this example, amoxicillin is the result being assessed and antibiotic 'X' refers to any other antibiotic.

### Primary outcome:

The number of antimicrobial susceptibility results that 'should' spur action by a clinician on the day that actual first-line AST results were reported (in green on Figure 5).

### Secondary outcomes:

5. The number of days until a result that 'should' spur action by a clinician (in green on Figure 5).
6. The number of antimicrobial susceptibility results that 'could' spur action by a clinician on the day that actual first-line AST results were reported (in yellow on Figure 5).
7. The number of days until a result that 'could' spur action by a clinician (in yellow on Figure 5).

8. The projected health economic cost per specimen, including laboratory (e.g., consumable cost) and patient (e.g., drug toxicity, clinical failure) measures guided by the above criteria.

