## ADAPT-AST Protocol

[figure not shown]

Figure 1: Current laboratory workflows fail to make use of past information related to the patient or the patient's immediate environment to make decisions about susceptibility testing, which may lead to delays in appropriate decision making. In low prevalence AMR settings, testing contributes little to clinical care.

[figure not shown]

Figure 2: In highly-prevalent AMR settings, a second round of susceptibility testing is required before appropriate antimicrobials are identified and therapy is changed. Each additional panel of susceptibility testing typically incurs at least 24 hours of delay.

This standard practice results in the provision of susceptibility information for clinicians which is:

a) Imprecise

Some laboratories in high income settings can test very large panels of antimicrobials immediately at day one (for example, the ThermoFisher® Sensititre™ Gram Negative MIC Plate tests 22 antimicrobials), but more commonly, and particularly in low or middle income (LMIC) settings, a selected subset of antimicrobials is tested at day one to save resources (for example, the MAST URI® system used in Liverpool Clinical Laboratories [LCL] tests a 7-antimicrobial panel) (4–6). There is currently a ‘one-size-fits-all’ approach to this testing, where a standard panel of antimicrobials are initially tested against urinary pathogens. These panels do not adapt for previous resistance patterns, antimicrobial prescribing, or demographic information despite their potential impact on the likelihood of susceptibility to various agents(7).

b) Inefficient

When the standard panel tested yields no appropriate antibiotics for the clinician to use, a ‘second line’ standard panel of antibiotics will then be tested. This process unnecessarily consumes the time of laboratory staff and requires additional resources to those used to set up the initial unusable panel of antimicrobials. Lack of information related to appropriate oral or outpatient parenteral antimicrobial therapy (OPAT) treatment options delays early discharge with patients required to stay in hospital to receive high-frequency intravenous (IV) antibiotic regimens(8).

c) Inequitable

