## **3.3 Development and Clinical Evaluation of ADAPT-AST in a simulated clinical setting**

### **3.3.1 AST Decision Making Algorithm Development**

The final stage of the project will be evaluating the potential clinical and resource impact of the testing framework on the same 20% of samples used in the testing dataset above. To do this, a clinically suitable AST decision making model first will need to be developed. Comparison of a range of algorithmic approaches is likely to be required, but the aim of the first decision model trialled will be to select 7 antimicrobials for testing (the number in the standard first-line panel currently tested under existing LCL SOPs). The antimicrobials that will be initially eligible for AST selection are those for which probability calculations will be outputted, listed above in Table 2.

The first prioritisation approach trialled will be to rank antimicrobial choices in descending order of susceptibility uncertainty except for cefpodoxime and cefoxitin, then to apply an algorithm in Figure 4 to ensure that a mixture of oral and intravenous agents is tested.

[figure not shown]

Figure 4: Algorithm used to select 7 antimicrobials from the sorted shortlist.

\*Amoxicillin, Amoxicillin-Clavulanate, Aztreonam, Cefalexin, Ceftazidime, Phenoxycephalothin, Piperacillin-tazobactam.

Cefpodoxime or cefoxitin are not used as treatments in the local area, but resistance to either antimicrobial indicates a high probability of resistance mechanisms which preclude use of some beta lactams (BL) and beta-lactam-beta-lactamase-inhibitor combinations (BL-BLIC)(57,58). Therefore, the algorithm will also be designed for cefpodoxime and cefoxitin to only be tested when their susceptibility is sufficiently uncertain (a defined classification threshold will be calculated for this) and there is a chance of the affected BLs / BL-BLICs, cefpodoxime and cefoxitin all being tested as part of the panel of 7.

No additional weighting, ranking or exclusion criteria will initially be applied, but depending on evaluation based on a priori microbiology / clinical / health economic knowledge, measures may need to be taken to further steward the AST choices. These may include exclusion of certain antimicrobial choices which are less practically useful for UTI but for which resistance uncertainty may be high (e.g., teicoplanin) or algorithmic prioritisation/exclusion/weighting measures for factors such as WHO

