### **3.3.2 Outcomes**

Outcomes will be assessed and compared between the 7-result AST panels provided by ADAPT-AST algorithms and those provided by standard of care algorithms based on LCL current SOPs as of 2023, both of which will be run on every available specimen. Susceptibility information will be assessed alongside drug allergies, renal function, drug interactions to characterise results that 'should', 'could', and cannot be actioned by the clinician. Computer algorithms will be written to perform this assessment in line with the schema in Figure 5 (amoxicillin provided as an example).

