### **3.3.3 Statistical Analysis**

A chi square goodness of fit test will be conducted to determine whether the counts of, and number of days until, 'should' and 'could' action results follow a Poisson distribution; if so, a one-sample exact Poisson test will be run to determine whether the mean number of 'should' and 'could' action results per specimen and the number of days to these results using ADAPT-AST would be different from the expected number using the LCL SOP. The mean financial cost per specimen will be analysed either with a single-sample paired t-test or Wilcoxon signed-ranks test depending on whether the data are normally distributed.

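### The two days-to-result secondary outcomes have no value for specimens that never yield an actionable result, and the planned test on days has no way to include them

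*Protocol*

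**What the plan says.** Protocol 3.3.2 has four secondary outcomes, two of which are times: "The number of days until a result that 'should' spur action by a clinician" and "The number of days until a result that 'could' spur action by a clinician". The same section says that computer algorithms will use susceptibility, allergy, renal function and interactions "to characterise results that 'should', 'could', and cannot be actioned by the clinician". A panel can therefore contain no 'should' result, or no 'could' result.

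Section 3.3.3 first checks whether the counts and the days fit a Poisson distribution. If they do, a one-sample exact Poisson test asks whether "the number of days to these results using ADAPT-AST would be different from the expected number using the LCL SOP". No section gives a score, cap or censoring rule for a specimen without a qualifying result. Section 3.3.4 discusses missing prescribing data and untested agents, but not this.

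On later panels, section 1.1 says of current practice that, when the first panel offers nothing appropriate, a second-line "standard panel of antibiotics will then be tested". The legend of Figure 2 adds: "Each additional panel of susceptibility testing typically incurs at least 24 hours of delay". For ADAPT-AST, section 3.3.1 says that "the aim of the first decision model trialled will be to select 7 antimicrobials for testing", and the text describes no follow-on round. Section 3.3.2 describes what is compared as "7-result AST panels provided by ADAPT-AST algorithms and those provided by standard of care algorithms", which reads as one panel in each arm.

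**The concern.** A time-to-result outcome needs a rule for specimens in which the result never comes. Without one, the comparison of days most naturally rests on the specimens that did yield a result. That subset is selected by the outcome itself and differs between the arms. An arm can then look faster because its difficult specimens have dropped out.

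The specimens most likely to drop out carry resistant organisms, which are the ones the system is meant to help. Timeliness of decision making is part of project question 2, and these two outcomes address it most directly. The point does not depend on whether a Poisson model suits the data. Any test on days meets the same gap.

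**Working it through.** The protocol gives no expected value, effect size or power for days, so there is no figure to reproduce. All shares below are assumptions for illustration.

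**Inputs**
- First panel reported on day 1 in both arms (assumed).
- Second panel one day later, on day 2 (from the 24-hour minimum in the Figure 2 legend).
- SOP: 70% resolved on day 1, 20% on day 2, 10% never (assumed).
- ADAPT-AST: 65% resolved on day 1, 35% never, with one panel only (assumed; this is one of the possible readings).

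**Reading 1: only the SOP arm has a second panel**

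Mean among specimens with a result = (sum of share × day) / share resolved.
- SOP: (0.70×1 + 0.20×2) / 0.90 = 1.10 / 0.90 = 1.22 days.
- ADAPT-AST: (0.65×1) / 0.65 = 1.00 day.

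ADAPT-AST looks faster, although it resolves fewer specimens on day 1 (65% v 70%) and overall (65% v 90%). Its mean stays at 1.00 whatever its success share, because every specimen it resolves is resolved on day 1.

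Mean over all specimens, with unresolved ones scored at day 3:
- SOP: 0.70×1 + 0.20×2 + 0.10×3 = 1.40 days.
- ADAPT-AST: 0.65×1 + 0.35×3 = 1.70 days.

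The direction reverses. Coding unresolved specimens as 0 days would not repair it: SOP 1.10 v ADAPT-AST 0.65, which again favours the arm with fewer results.

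**What the stated test would show.** Section 3.1.3 estimates at least 250,000 specimens, and 20% are used for evaluation: 50,000. ADAPT-AST would have 0.65 × 50,000 = 32,500 specimens with a result and 32,500 days in total. At the SOP rate the expected total is 32,500 × 1.10/0.90 = 39,722. The gap of 7,222 is about 36 Poisson standard deviations (√39,722 ≈ 199). The misleading direction would be highly significant.

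**Reading 2: one panel in each arm**

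Every resolved specimen has its first-panel day, so both means are 1.00 for any success shares. Days among resolved specimens cannot tell the arms apart.

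**Dependence on the horizon**

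With horizon H, the SOP mean is 1.10 + 0.10×H, and the ADAPT-AST mean with day-1 share a is a + (1 − a)×H. They are equal at a = (0.90×H − 1.10) / (H − 1).

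| Horizon | SOP mean | Break-even a | ADAPT-AST mean at a = 0.65 | ADAPT-AST mean at a = 0.75 |
|---|---|---|---|---|
| Day 2 | 1.30 | 0.70 | 1.35 | 1.25 |
| Day 3 | 1.40 | 0.80 | 1.70 | 1.50 |
| Day 8 | 1.90 | 0.87 | 3.45 | 2.75 |

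At a = 0.75 the direction changes between day 2 and day 3, so the horizon is a real choice.

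**The case against.** A reader might infer that ADAPT-AST has no second panel, and hence that the bias must run in its favour. The documents do not establish this. Section 3.3.1 calls the seven-agent selection only the first model to be trialled. Figures 3 to 5, which hold the workflow, selection and classification schemas, are not available here. Section 3.3.2 describes both arms as seven-result panels, and the second-line panel appears only in the background. A days outcome makes little sense if each arm reports on one day, so later rounds may be intended. If both arms have them, the structural asymmetry goes. This objection stands: the direction of bias is conditional.

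Nor does section 3.3.3 say that specimens without a result are dropped, and a statistical analysis plan could add a scoring rule. That is fair, but the protocol defines these outcomes and names their test, and neither accommodates such specimens. The Poisson test is conditional on a fit test, but that also needs a value for each specimen.

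Finally, the two count outcomes score a specimen with no qualifying result as zero, so an arm with fewer actionable first-day results would be exposed there. This limits the harm but does not make the days outcomes interpretable.

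**Conclusion.** The gap is real and does not depend on how later panels are handled: two of the four secondary outcomes are undefined for specimens that the protocol itself allows, and the stated test on days cannot include them. The consequence does depend on the reading. With a second panel in the SOP arm only, and the assumed shares, the comparison reverses from 1.22 v 1.00 to 1.40 v 1.70 days. With one panel in each arm, the outcome carries no information. With later panels in both arms, the structural asymmetry goes, but unresolved specimens still have no value.

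The example shows that a misleading direction is possible, not that it will occur, since no share in it comes from the protocol. The primary outcome is a count with a natural zero and is unaffected. This should be settled before the simulated comparison is run, but it does not threaten the main result.

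**What to change.** In sections 3.3.2 and 3.3.3:

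- Give every test specimen a value in both arms by scoring those without a qualifying result at one common, prespecified horizon.
- Replace the one-sample test on days with the paired within-specimen difference in restricted mean days over all test specimens. Both algorithms run on every specimen, so the pairs exist.
- Report the share of specimens with no 'should' result and with no 'could' result in each arm beside the days.
- State whether panels after the first are simulated, with the same convention in both arms. If neither arm has one and the first-panel day is common, the restricted mean difference is only the difference in unresolved shares multiplied by (H − 1). The shares then suffice.

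The cost is protocol wording and a modest change to the analysis code. Simulating follow-on panels would cost more, because section 3.3.4 accepts that some agents were never tested and a later panel may call for results that do not exist. The drawback of a horizon is that the direction can depend on it, so it must be fixed in advance and varied in a sensitivity analysis.

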### **3.3.3 Statistical Analysis**

A chi square goodness of fit test will be conducted to determine whether the counts of, and number of days until, 'should' and 'could' action results follow a Poisson distribution; if so, a one-sample exact Poisson test will be run to determine whether the mean number of 'should' and 'could' action results per specimen and the number of days to these results using ADAPT-AST would be different from the expected number using the LCL SOP. The mean financial cost per specimen will be analysed either with a single-sample paired t-test or Wilcoxon signed-ranks test depending on whether the data are normally distributed.

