### **3.1.3 Sample size**

The main sample size consideration is the volume of data required to train the BCI algorithm; this will be higher than the sample size required to provide 80% power to detect a significant (e.g.,  $p < 0.05$ ) difference between groups in the simulated interventional study. For the binary LR techniques like that used to develop the predictive model, however, much larger sample sizes are required to provide predictive accuracy(43). Given that a range of BCI techniques are likely to be trialled and that most of the variation will be taking place in a small proportion of samples, data pertaining to a large number of specimens will be required. All eligible patients who have grown an organism in a urine specimen during the a five year period from 17th May 2017 will be recruited for the development and testing of the predictive algorithm. This period has been chosen to provide a balance between strength of model, the amount of data available, computational power required and 'concept drift' i.e., changes in susceptibility patterns and laboratory practice over time; the most recent AST practice change in LCL was implemented 17th May 2017(44). This period will provide an estimated sample size of at least 250,000 specimens, which will pertain to fewer patients than that number as some will have had urine specimens sent more than once.

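### The primary test runs only if a chi-square test accepts a Poisson fit, which about 50,000 panel counts will very likely fail, and no other analysis is named

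*Protocol*

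**What the plan says.** The primary outcome (Protocol section 3.3.2) is "The number of antimicrobial susceptibility results that 'should' spur action by a clinician on the day that actual first-line AST results were reported". The comparison is "between the 7-result AST panels provided by ADAPT-AST algorithms and those provided by standard of care algorithms" that follow the laboratory's current procedures, with both run on each specimen.

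Section 3.3.3 sets the analysis of the counts and the days. It opens "A chi square goodness of fit test will be conducted to determine whether the counts of, and number of days until" a 'should' or 'could' result "follow a Poisson distribution; if so, a one-sample exact Poisson test will be run". This one sentence covers 'should' and 'could' counts and the days to each, so it carries the primary outcome and secondary outcomes 1 to 3 of the Study Summary. It has no 'if not'. The following sentence, on cost, does have both branches: "either with a single-sample paired t-test or Wilcoxon signed-ranks test depending on whether the data are normally distributed".

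On size, section 3.1.3 states: "This period will provide an estimated sample size of at least 250,000 specimens". Section 3.3.1 places the evaluation on the 20% test set.

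**The concern.** A preliminary test that decides whether the main analysis happens must have an outcome on both sides. Here only acceptance leads anywhere. The variable is also one that gives little reason to expect acceptance: the number of qualifying results on a small fixed panel is a sum of a few yes/no outcomes that share a patient and usually an organism. A Poisson law follows from neither feature. With tens of thousands of specimens, a goodness-of-fit test detects departures too small to matter in practice.

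At stake is whether the primary outcome has a prespecified analysis. If the fit is rejected, the analysts must pick a method with the counts already in front of them.

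**Working it through.** **Inputs.** At least 250,000 specimens (section 3.1.3); 20% used for evaluation (section 3.3.1); 7 results per panel (section 3.3.2); significance level 0.05 (given as an example in section 3.1.3). The 250,000 is an estimate of available data. No effect size or rate is attached to it, so there is no power calculation to reproduce.

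**Evaluation set.** 0.20 × 250,000 = 50,000 specimens.

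**Method.** Fit a Poisson by the sample mean, pool tail cells until each expected count is at least 5, and use cells minus 2 degrees of freedom. The approximate rejection probability comes from a noncentral chi-square with noncentrality N × Σ(p − q)²/q, where p is the true and q the Poisson cell probability. Simulation was used as a check. The protocol does not give the true distribution, so a range is assumed.

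**Counts, independent results: Binomial(7, p), N = 50,000.**

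| p | Mean | Noncentrality | Rejection probability |
|---|---|---|---|
| 0.01 | 0.07 | 2.34 | 0.33 |
| 0.02 | 0.14 | 9.99 | 0.81 (84% to 87% in simulation) |
| 0.03 | 0.21 | 22.4 | 0.99 (100% in simulation) |
| 0.05 | 0.35 | 63.1 | 1.00 |
| 0.30 | 2.10 | about 2,500 | 1.00 |

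At p = 0.30 the variance is 7 × 0.3 × 0.7 = 1.47 against a mean of 2.1. A Poisson with that mean expects about 74 of 50,000 specimens above 7.

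**Counts, correlated results: beta-binomial(7, p, ρ).** With p from 0.02 to 0.5 and ρ from 0.05 to 0.3, rejection is 1.00 in all 24 combinations.

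**When the gate could pass.** Variance equals mean when (1 − p)(1 + 6ρ) = 1, that is ρ = p/[6(1 − p)]. At p = 0.02 this is 0.02/5.88 = 0.0034; at p = 0.10 it is 0.10/5.4 = 0.0185. In simulation this tuned case is rejected in 5.5% of runs at mean 0.14, 4.5% at 0.20, 10% at 0.35, 17% at 0.50 and 45.5% at 0.70; at means of 1.4 or more it is rejected in 100%. A Poisson merely truncated at 7 is rejected about 5% of the time with parameter 1 or less, about 53% at 1.5, and always at 2 or more.

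**Sensitivity of the gate.** A variance/mean ratio that differs from 1 by about 2.80 × √(2/50,000) = 0.018 is detected with 80% power.

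**Days to result.** Assume counting from day 1, with 90% on day 1 and 10% on day 2. The mean is 1.1, the variance 0.9 × 0.1 = 0.09, and the ratio 0.09/1.1 = 0.08. With values of 1 to 3 days and 60%, 80% or 95% on day 1, rejection is 1.00 each time. Two-valued distributions are also always rejected if the count starts at 0.

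**If the gate were ignored.** The ratio of the Poisson standard error to the true one is 1/√[(1 − p)(1 + 6ρ)], specimens taken as independent. At p = 0.6, ρ = 0: 1/√0.4 = 1.58. At p = 0.2, ρ = 0.3: 1/√(0.8 × 2.8) = 0.67.

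**What a p-value would flag.** For a one-sample Poisson test at mean 2, the difference detectable with 80% power is 2.80 × √(2/50,000) = 0.018 results per specimen, about one result per 56 specimens.

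**The case against.** The strongest reply is that the count distribution is unknown. The rule for a 'should' result sits in Figure 5, and no expected number is given. The caption of Figure 1 says testing adds little to care where resistance is uncommon, so a low mean is possible. This stands. A reader might infer from the 7-result panel that the count cannot pass as Poisson and that the gate is certain to fail. The documents do not support that: at low means the cap is nearly undetectable, and the tuned and truncated cases above usually pass. Passing does, however, need very rare results or a variance almost equal to a low mean.

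The cap itself is also not certain. Section 3.1.5 enters each organism from a mixed growth separately and only trials a composite result, so a specimen could exceed 7 if results are counted per organism. That would be another departure from Poisson and does not rescue the gate.

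A reader might also infer that Poisson standard errors would simply be too large. That holds only for independent results; within-specimen correlation can reverse it.

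Finally, a fallback is often left to a statistical analysis plan, and the study is retrospective and simulated, with no patient exposed. The second part limits the harm, and with 50,000 specimens most sensible methods would agree unless the effect is tiny. The first part does not remove the point. The protocol itself fixes the pre-test, the condition and the single test, and shows in the next sentence that it can state two branches.

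**Conclusion.** The point holds. That the gate has one exit is plain from section 3.3.3 and depends on no calculation. That the exit will very likely be closed rests on assumed distributions: rejection is about 84% for independent results at p = 0.02, essentially certain from p = 0.03, certain in every correlated case on the grid, and certain for the assumed days distributions. The exceptions are very rare 'should' results, or counts whose variance almost equals a low mean (about 0.5 or less in the tuned beta-binomial case).

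Outside those exceptions, a team following the text reaches the primary outcome with no specified test. Setting the gate aside and running the Poisson test anyway would not be safe either, since its standard error could be between about 0.67 and 1.6 times the true one over p of 0.2 to 0.6 and within-specimen correlation of 0 to 0.3.

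**What to change.** Delete the goodness-of-fit step and the one-sample Poisson test from section 3.3.3. In their place, name one analysis in advance: the mean within-specimen difference (ADAPT-AST minus the laboratory procedure) with a 95% bootstrap confidence interval. It uses the fact that both algorithms run on the same specimens and needs no assumed count distribution.

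Resample patients, not specimens. Section 3.1.3 says some patients contribute several specimens, so a specimen-level bootstrap would likely give an interval that is too narrow.

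Judge the interval by the size of the difference, preferably against a stated smallest worthwhile difference, because a p-value alone would flag about 0.02 results per specimen. Say whether mixed growth is counted per organism or per specimen. For the days outcomes, state the day from which counting starts and how a specimen with no actionable result is handled.

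The cost is a rewritten sentence or two and trivial computing. No further data are needed. The change should be made before any evaluation results are examined.

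### The primary outcome is tested against the SOP mean as if it were a known constant, although both algorithms run on the same specimens

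*Protocol*

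**What the plan says.** Protocol section 3.3.3 sets the analysis in two stages. First, "A chi square goodness of fit test will be conducted to determine whether the counts of" and the days to 'should' and 'could' results are Poisson. If they are, "a one-sample exact Poisson test will be run to determine whether the mean number of 'should' and 'could' action results per specimen" and the days to those results under ADAPT-AST "would be different from the expected number using the LCL SOP". This covers the primary outcome ('should' results on the day of first-line reporting) and three of the four secondary outcomes. The fourth, cost per specimen, gets a "single-sample paired t-test or Wilcoxon signed-ranks test".

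Section 3.3.2 describes the design: "Outcomes will be assessed and compared between the 7-result AST panels provided by ADAPT-AST algorithms" and those from the laboratory's current SOP, "both of which will be run on every available specimen". The evaluation uses the "same 20% of samples used in the testing dataset above" (section 3.3.1). On patients, section 3.1.3 notes that "some will have had urine specimens sent more than once".

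**The concern.** A one-sample Poisson test compares an observed count with a rate fixed in advance. No such rate exists here. The SOP's expected number is obtained by running the SOP algorithm on the evaluation specimens, and the protocol names no external source for it. The comparison is therefore between two estimates from the same specimens. The stated test ignores the sampling variance of the SOP mean and its correlation with the ADAPT-AST mean. It also treats repeat specimens from one patient as independent. Cost, measured on the same specimens, does get a paired test, so section 3.3.3 is inconsistent within itself.

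At stake is whether the p-value for the primary outcome, and any interval obtained by inverting the test, means what it says. The goodness-of-fit condition adds a second difficulty: if it fails, section 3.3.3 names no test for the primary outcome.

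**Working it through.** **Inputs from the protocol.** At least 250,000 specimens (section 3.1.3), of which 20% are used for evaluation (section 3.3.1): n = 0.20 × 250,000 = 50,000. Panel of 7 results (section 3.3.2). Level 5%, which section 3.1.3 gives only as an example; two-sided because section 3.3.3 asks whether the means differ. The protocol reports no calculated power or error rate for this comparison, so there is no figure to reproduce.

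**Inputs not given, assumed and varied.** Mean count λ, within-specimen correlation ρ between the two algorithms' counts, variance-to-mean ratio φ, and design effect D for repeat specimens.

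**Step 1: variance.** The test assumes variance λ/n. With equal means and equal dispersion, the difference between the two means has variance 2φ(1−ρ)Dλ/n. The ratio is R = 2φ(1−ρ)D. The real two-sided error is 2[1 − Φ(1.96/√R)], which equals 5% only at ρ = 1 − 1/(2φD).

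**Step 2: real error of the nominal 5% test, D = 1.**

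| ρ | 0 | 0.25 | 0.5 | 0.75 | 0.9 |
|---|---|---|---|---|---|
| R at φ = 1 | 2.0 | 1.5 | 1.0 | 0.5 | 0.2 |
| Poisson counts, φ = 1 | 16.6% | 11.0% | 5.0% | 0.6% | <0.01% |
| Simulated exact Poisson test, φ = 1 | 16.2% | 10.9% | 5.2% | 0.6% | 0.0% |
| φ = 0.7 | 9.8% | 5.6% | 1.9% | 0.1% | <0.01% |
| φ = 1.5 | 25.8% | 19.1% | 11.0% | 2.4% | 0.03% |
| Simulated test on the within-specimen difference, φ = 1 | 5.1% | 5.0% | 5.3% | 5.2% | 5.2% |

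The simulations used 20,000 runs, n = 50,000, λ = 2 and pairs built from a shared Poisson component. The last row uses the true standard error of the difference.

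**Step 3: repeat specimens.** With φ = 1, the correlation at which the error is 5% moves from 0.5 to 1 − 1/(2D): 0.60, 0.67 and 0.75 for D = 1.25, 1.5 and 2.

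**Step 4: size on the outcome scale (λ = 1.5, φ = 1, D = 1).** The stated test declares significance at a difference of 1.96 × √(1.5/50,000) = 0.0107 results per specimen. A paired test needs 1.96 × √(2(1−ρ) × 1.5/50,000): 0.0152 at ρ = 0 and 0.0048 at ρ = 0.9. For a true difference of 0.01 at ρ = 0.9, the standard error is √(0.2 × 1.5/50,000) = 0.00245. Power is then Φ((0.01 − 0.0107)/0.00245) ≈ 38% for the stated test and Φ(0.01/0.00245 − 1.96) ≈ 98% for the paired test. At a difference of 0.05, both exceed 99.9%.

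**Step 5: the goodness-of-fit condition, counts only.** Power of the chi-square test against a Poisson distribution with the same mean, n = 50,000, upper-tail cells merged to an expected count of at least 5, degrees of freedom = cells − 2. For Binomial(7, p) counts:

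| Mean | 0.02 | 0.05 | 0.1 | 0.2 | 0.35 |
|---|---|---|---|---|---|
| Noncentrality | 0.2 | 1.2 | 5.1 | 20.3 | 63.1 |
| Rejection | 7% | 20% | 51% | 98.6% | >99.99% |

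If specimens differ in their probability of an actionable result (beta-binomial), the outcome depends on the intraclass correlation. At 0.05, rejection exceeds 99.99% at every mean checked from 0.02 to 3.5. At 0.01 and mean 0.35 it is only 22%. There the cap and the heterogeneity nearly cancel: p = 0.35/7 = 0.05 and variance/mean = 0.95 × (1 + 6 × 0.01) ≈ 1.01.

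**The case against.** The strongest objection is that the one-sample test may never be reached. At a mean of 1.5, the goodness-of-fit test rejects with probability above 99.99% for Binomial(7, p) and for beta-binomial counts at intraclass correlations of 0.005, 0.01, 0.02 and 0.05. The step 4 figures then describe a test that is not run, and the gate is the operative problem. That stands as a limit on step 4. It does not rescue section 3.3.3, which in that case names no test for the primary outcome.

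Second, the error need not be inflated. Both panels are scored on the same specimens and may share agents, so a high correlation is plausible; the test would then be conservative and lose power. The 0.5 crossover also depends on φ = 1 and no clustering. For Binomial(7, p) at mean 1.5, φ = 1 − 1.5/7 = 0.79, the crossover is 0.36, and the error at zero correlation is 11.8%. All of this stands: the calibration is wrong in a direction the protocol does not allow one to determine.

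Third, with about 50,000 specimens the conclusion changes only for small differences. That stands and limits the severity.

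Fourth, a fallback test, clustering and specimens without an actionable result are often left to a SAP. That is fair for those details taken alone. It does not cover the main point, because section 3.3.3 itself fixes the test, its comparator and its precondition.

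**Conclusion.** The concern holds and should be fixed. A one-sample test is prescribed for paired data, and this follows from sections 3.3.2 and 3.3.3 without any assumed input. The p-values for the primary and three of the four secondary outcomes do not hold their nominal level, except where the correlation happens to sit at the crossover. For Poisson counts without clustering, the real error runs from 16.6% at zero correlation to practically nil at 0.9, and the true standard error from 1.41 to 0.45 times the assumed one. Means, correlation, dispersion and clustering are assumptions shown as ranges. Large differences would be detected by either test; small differences and interval widths are affected. Failure of the Poisson check is likely at moderate means but not certain. The gate calculation covers counts only, and none was done for days to result.

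**What to change.** Reword section 3.3.3:

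- Remove the goodness-of-fit condition and the one-sample Poisson test.
- For each specimen, take the ADAPT-AST minus SOP difference in 'should' results, and likewise in 'could' results. Report the mean difference with a 95% CI from a bootstrap that resamples patients, or from patient-clustered standard errors.
- Use the same paired approach for days to result, and state how specimens that never yield an actionable result are handled before the test-set comparison is run.

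The cost is a rewritten paragraph and a few lines of code. Both algorithms are already to be run on every specimen, so no new data are needed.
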